9.5 Protocol Deviations

Significant protocol deviations that could potentially affect the efficacy or safety conclusions of the study will be identified prior to database lock and unblinding of individual subject treatment information. Significant protocol deviations may include, but are not limited to:

- Randomly assigned subjects who did not satisfy selected inclusion and exclusion criteria
- Randomly assigned subjects who developed withdrawal criteria during the study but were not withdrawn
- Subjects who were randomized incorrectly including subjects of the same household who are randomized to different treatments
- Subjects who received the wrong treatment
- Subjects where the subject/site staff were unproperly unblinded
- Week 12 Lesion Count not performed
- Subjects who received an excluded concomitant treatment.

The decision on the criteria for whether a subject is excluded from the PP Population will be made during the data review meeting prior to unblinding and database lock. Reasons for exclusion of a subject from the analysis will be listed.

A listing of all protocol deviations including the deviation designation (major or minor and significant or not), category, and indication of whether the deviation led to an exclusion of a subject from the PP Population will be presented in a data listing.

Major and significant protocol deviations will be summarized by deviation category and treatment group.

9.6 Medical History

Medical history verbatim terms in the eCRFs will be mapped to system organ classes and preferred terms using the Medical Dictionary for Regulatory Activities (MedDRA) Version 22.0. Subject incidence of unique medical history terms by MedDRA system organ class and preferred term will be presented. The summary will be ordered by descending order of incidence of system organ class and preferred term within each system organ class.

9.7 Prior and Concomitant Medications

Prior and concomitant medication verbatim terms in the eCRFs will be mapped to anatomical/therapeutic/chemical (ATC) class and preferred names using the WHO Drug Global B3 (version March 2019). Prior medications are those medications started prior to the first application of study drug. Concomitant medications are those medications started on or after the date of first application of study drug or medications started prior to initial application of study

drug and continued during the study. A medication can be classified as both prior and concomitant. If it cannot be determined whether the medication was a prior (or concomitant) medication due to a partial start or stop date, then it will be counted as both prior and concomitant; see [Appendix B](#) for the imputation of missing dates algorithm.

Prior and concomitant medications will be summarized for each treatment by WHODrug Global ATC class Level 3 and preferred name. These summaries will present the number and percentage of subjects using each medication. Subjects may have more than 1 medication per ATC class and preferred name. At each level of subject summarization, a subject is counted once if he/she reported 1 or more medications at that level. Each summary will be ordered by descending order of incidence of ATC class and preferred name within each ATC class.

10. EFFICACY ANALYSES

The primary efficacy analysis will be based on the ITT Population. Additional supportive efficacy analyses will be performed using the PP Population.

10.1 Efficacy Endpoints

The primary efficacy endpoint is the proportion of subjects with complete clearance of all treatable MC at Week 12.

The secondary efficacy endpoint is the proportion of subjects with complete clearance of all treatable MC at Week 8.

Complete clearance is defined as having a total number of lesions count of 0.

The exploratory endpoints are the following:

- Proportion of subjects with complete clearance of all treatable MC at Week 2 and Week 4 visits
- Proportion of subjects achieving at least a 95% reduction from Baseline in the number of all treatable MC at each visit (Weeks 2, 4, 8, 12)
- Proportion of subjects achieving at least a 90% reduction from Baseline in the number of all treatable MC at each visit (Weeks 2, 4, 8, 12)
- Proportion of subjects achieving at least a 75% reduction from Baseline in the number of all treatable MC at each visit (Weeks 2, 4, 8, 12)
- Percent change from Baseline in number of treatable MC at each visit (Weeks 2, 4, 8, 12)
- Change from Baseline in number of treatable MC at each visit (Weeks 2, 4, 8, 12)
- Proportion of subjects who have a recurrence of MC after the first visit at which complete clearance was observed, defined as the total lesion count being greater than 0 at any point after achieving a count of 0

- Time to complete clearance of all treatable MC, defined as the days between the date of first dose and the first date of clearance. Subjects who do not achieve complete clearance will be censored at the date of the last lesion count assessment.
- Proportion of subjects with scarring, defined as an answer of Yes to either question on the Scarring/Keloid Assessment eCRF page: “Was the presence of a scar > 1 mm deep and/or 5 mm wide noted?” or “Was the presence of a scar noted?”, after clearance of lesion(s) at each visit (Weeks 4, 8, 12, 24)
- Proportion of subjects with keloid or hypertrophic scar, defined as an answer of Yes to the Scarring/Keloid Assessment eCRF page question “Was the presence of a keloid or hypertrophic scar noted?”, after clearance of lesion(s) at each visit (Weeks 4, 8, 12, 24)
- Change from Baseline of the composite score from age-matched (at Baseline) Dermatology Life Quality Index (DLQI) or Children’s Dermatology Life Quality Index (CLDQI) assessment at Week 12
- Subject-reported spread to household members as measured by any new occurrence of MC in household members of subjects at each visit (Weeks 2, 4, 8, 12, 16, 20, 24)

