If the investigator determines all lesions are cleared at a clinic visit, the treatment may stop. At Weeks 2, 4, and 8, the investigator will determine if new lesions have occurred since the last visit, and the subject or caregiver will be instructed by the investigator to re-initiate treatment. If treatment is stopped due to clearance, subjects will continue regularly scheduled visits through Week 24/ET2. Subjects will be followed for recurrence/new lesions until Week 24. For the purpose of this study, a recurrence of MC will be documented as an AE.

1.2.2 *Dose Selection Rationale*

Novan completed a Phase 2 ascending dose study of SB206 in 256 subjects with MC. The primary endpoint for Study NI-MC201 was the proportion of subjects in the modified intent-to-treat population who achieved complete clearance of all MC lesions at Week 12. In this analysis, 8%

BID and 12% QD groups of SB206 were statistically significantly superior to vehicle in the proportion of subjects with complete clearance at Week 12: 20.0% (vehicle BID/QD combined), 41.0% (8% BID: $p=0.028$), and 41.9% (12% QD: $p=0.024$). The difference in proportion (95% CI) from vehicle was statistically significant for 8% BID (0.206 [0.022, 0.389], $P = 0.028$) and 12% QD (0.204 [0.027, 0.381], $P = 0.024$). A sensitivity analysis of the primary efficacy endpoint in the ITT population produced results consistent with the primary analysis results. Secondary and exploratory efficacy endpoints also support selection of 12% QD. In the Phase 2 study, 7 subjects were discontinued from treatment with the study drug due to an AE, all in active treatment groups (3 subjects in the 4% BID group; 2 in the 8% BID group; and 2 in the 12% BID group). Treatment discontinuation was due to application site reactions in 6 of these subjects and to worsening MC in the other. No subject discontinued treatment due to AEs in the 12% QD group.

Based on totality of the data, SB206 12% QD was selected for this Phase 3 study.

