Subjects will visit the clinic at Screening/Baseline, Week 2, Week 4, Week 8, Week 12, and Week 24. Subjects will be contacted via phone on Day 2 to collect subject information on early dose reactions. At Weeks 16 and 20, subjects will be contacted via phone to capture information regarding MC recurrence and AEs; at Week 24, the subject will be seen at the site for a final study visit. Subjects who discontinue the study prior to the Week 12 visit due to adverse events or other reasons will be asked to complete the Week 12 visit assessments; this will be recorded as an Early Termination (ET1) visit. No study drug treatment will be provided after the Week 12 visit. Subjects who discontinue from the study after Week 12 but prior to Week 24 will be asked to come to the site to complete Week 24 assessments; this visit will be recorded as an ET2 visit.

Safety assessments include BOTE Inflammation Scores, Local Skin Reaction Scores (LSRs), adverse event collection, including scarring/keloid and urine pregnancy tests (UPTs). Safety assessments will be completed at specified site visits through Week 12. After Week 12, safety information for ongoing AEs and new AEs will be collected, along with information regarding MC recurrence. For the purpose of this study, a recurrence of MC will be documented as an AE.

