If a subject's treatment is discontinued by the investigator or the subject because of an AE, that AE should be indicated as the reason for treatment discontinuation. All subjects will be encouraged to remain in the study throughout the 24-week study duration.

In the event of suspected allergic contact dermatitis, photographs may be taken of the affected area(s) and transmitted to the CRO medical monitor for review prior to initiating patch testing.

When approximately 200 subjects (cumulative across studies NI-MC302 and NI-MC302) have completed 4 weeks of treatment, a Data Safety Monitoring Board (DSMB) will review all available unblinded safety data (including completed patch testing results).

Table 1: Schedule of Assessments

	Screening	Treatment					
	Screening ¹ (Day -14 to Day 1)	Visit 1 ¹ Baseline (Day 1)	V2 Telephone Contact (Day 2)	Visit 3 ² Week 2 (Day 15 ±3)	Visit 4 ² Week 4 (Day 29 ±5)	Visit 5 ² Week 8 (Day 57 ±5)	Visit 6 ² Week 12/ ET1 (Day 85 ±5)
Informed Consent (Assent)	X						
Demographics	X						
Medical and Medication History	X						
Lesion Count or Recurrence	X	X		X	X	X	X
Physical Exam		X					X
Urine Pregnancy Test ³	X	X			X	X	X
BOTE Inflammation Score ⁴		X (pre-dose)		X	X	X	X
Local Skin Reactions (LSR) (post-dose) ⁴		X		X	X	X	X
Scarring/Keloid Assessment					X	X	X
DLQI/CDLQI ⁵		X					X
Review of Inclusion/Exclusion Criteria	X	X					
Drug Dispensed		X			X	X	
Dispense Subject Diary		X		X	X	X	
Review Subject Application Instructions		X		X	X	X	
In Clinic Study Drug Application ⁶		X		X	X	X	X
Review Study Drug Compliance				X	X	X	X
Collect Study Drug					X	X	X
Collect Subject Diary				X	X	X	X
Record Adverse Event (AE) and Concomitant Medication (CM) Changes ⁷		X	X	X	X	X	X

	Safety Follow-up		
	Visit 7 ² Week 16 Telephone Contact (Day 113±5)	Visit 8 ² Week 20 Telephone Contact (Day 141±5)	Visit 9 ² Week 24/ ET2 (Day 169±5)
Scarring/Keloid Assessment			X
Record Adverse Event (AE) and Concomitant Medication (CM) Changes ⁷	X	X	X

¹Screening and Baseline may occur on the same day. If this occurs, lesion count and review of inclusion/exclusion criteria will only occur once. If two members of the same household qualify for study participation, they must be randomized on the same day.

²All visit dates are in reference to Baseline, e.g. Week 2 occurs 14 days after Baseline Visit.

³Females 9 years of age and older.

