⁴BOTE Inflammation Score will be assessed pre-dose at Baseline, and post-dose from Visit 3 through Visit 6. LSRs will be performed post-dose at each applicable visit.

⁵DLQI will be administered for subjects age 16 and older. The CDLQI will be administered for subjects ages 4 to age 16. If a subject turns 16 during the course of the study, the CDLQI will continue to be administered for consistency.

⁶Study drug application will occur in clinic at each study visit, from Baseline through Visit 5. Subjects will not apply the study drug at home on days where a study visit will occur.

⁷At Screening, subjects should be asked if any household members currently have MC. In addition to recording AE and CM changes, subjects should be asked if there are any new occurrences of MC in household members of subjects at each visit, except Screening and Day 2.

NOTE: Unscheduled visits are permitted as needed for medical reasons.

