6.2.6 Visit 5/Week 8 (Day 57 ±5)

The following procedures must be performed and recorded at the Week 8 visit.

1. Obtain pregnancy test and evaluate results, as applicable. If pregnancy test is positive, the subject may continue in the study; however, study drug should be discontinued.
2. Perform lesion mapping and update lesion map with location for any new lesions.
3. Perform scarring/keloid assessment.
4. Weigh returned study drug and review study compliance.
5. Weigh, record, and dispense new supply of study product and dispense subject diary.

6. Review dosing instructions and have subject/caregiver apply daily dose in clinic using the newly dispensed kit.
7. Perform BOTE Inflammation Score (post-dose).
8. Perform Local Skin Reaction Assessment (post-dose).
9. Collect and record AE information for AEs reported.
10. Update concomitant medication information and confirm if any new occurrences of MC were reported in the subject's household.

6.2.7 *Visit 6/Week 12/ET (Day 85 ±5)*

The following procedures must be performed and recorded at the Week 12/ET1 visit.

1. Complete age-matched Dermatology Life Quality Index (DLQI) assessment, as applicable.
2. Obtain pregnancy test and evaluate results, as applicable.
3. Perform lesion mapping and update lesion map with location for any new lesions.
4. Perform scarring/keloid assessment
5. Perform a brief physical examination.
6. Subject/caregiver administer final dose of study drug from previously dispensed kit.
7. Perform BOTE Inflammation Score (post-dose).
8. Perform Local Skin Reaction Assessment (post-dose).
9. Weigh returned study drug and review study compliance.
10. Collect and record AE information for AEs reported.
11. Update concomitant medication information and confirm if any new occurrences of MC were reported in the subject's household.

6.2.8 *Visit 7/Week 16 and Visit 8/Week 20 (Day 113 +/- 7 days; Day 141 +/- 7 days)*

The following procedures must be performed and recorded at the Week 16 and Week 20 visits. It is expected that these visits should be done by telephone.

1. Collect and record information for new and ongoing AEs, including recurrence of MC.
2. Update concomitant medication information.

6.2.9 *Visit 9/Week 24 (Day 169 +/- 7 days)*

The following procedures must be performed and recorded at the Week 24 visit.

1. Perform scarring/keloid assessment.
2. Collect and record information for new and ongoing AEs, including subject recurrence of MC.

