7.1 Efficacy Assessments

7.1.1 *Molluscum Contagiosum Lesion Counts*

Molluscum contagiosum is a viral infection characterized by small, discrete, waxy, skin-colored, dome-shaped papules, an average of 3–5 mm in diameter. The papules may be umbilicated and contain a caseous plug. When the lesions are squeezed or traumatized, a creamy, grey-white material can be extruded. If the investigator cannot clearly differentiate the lesions as is the case for agminated (clustered lesions) this should be counted as one lesion. If the investigator can differentiate and count the umbilical tops separately, each lesion should be counted separately. The

investigator should be consistent with the method of recording agminated lesions throughout the study.

For the purpose of this clinical trial, only active MC lesions are counted. Treatable lesions are any active (raised, palpable) MC lesions that are dome-shaped, pearly and shiny white top centered papules that are at least 2 cm away from the ocular region.

All study personnel who will perform lesion counts must pass the study training including lesion count training. Training on how to accurately count the number of MC lesions will be provided.

Mapping of lesions: At every visit from Baseline through Week 12, all lesions should be recorded on the body map and will clearly note the location of each lesion or agminated lesion. The lesion map is intended to assist study personnel in performing lesion counting and scar/keloid assessment.

Definition of Clearance: For the purpose of this study, “clear” means resolution of the active (raised, palpable) treatable molluscum lesion(s). After resolution, the residual surface changes such as pitted scar (indentation) < 1 mm in depth at the molluscum lesion area (<5 mm in diameter), hyper or hypopigmentation may remain. As these are considered part of the normal healing, they will not be captured as adverse events. Refer to the lesion count training for details.

The same evaluator should perform lesion counts at Screening, Baseline, and Weeks 2, 4, 8 and 12/ET1. In the event that this is not possible due to unforeseen circumstances, a different evaluator may evaluate the subject. The evaluator must pass the study training including lesion count training. It is particularly important to ensure the same evaluator performs the Baseline and Week 12/ET1 for lesion count for a subject and also Baseline and Week 24/ET2 assessment for scarring/keloid scarring.

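### Recurrence is defined by lesion counts that stop at Week 12 although it is followed to Week 24 as an AE, and SAP 13.1 narrows the SAE summary without saying so

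*Combined protocol and SAP*

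**What the plan says.** The file holds three SAP versions. References here are to the last one (table shells Version 3.0); the recurrence definition is the same in all three.

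**Endpoint.** Protocol 3.3 lists, as exploratory, the proportion of subjects whose disease returns after the first visit at which they were clear. It sets no end time and does not tie recurrence to a lesion count. SAP 10.1 makes it operational as "defined as the total lesion count being greater than 0 at any point after achieving a count of 0".

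**Lesion counts.** Protocol 7.1.1: "The same evaluator should perform lesion counts at Screening, Baseline, and Weeks 2, 4, 8 and 12/ET1". In protocol Table 1 the row "Lesion Count or Recurrence" is marked from Screening to Week 12/ET1. The follow-up part of that table (Weeks 16, 20, 24) has rows only for scar/keloid and for AEs with concomitant medication. A note to the table adds: "Unscheduled visits are permitted as needed for medical reasons".

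**Recurrence follow-up.** Protocol 1.2.1: "Subjects will be followed for recurrence/new lesions until Week 24". Protocol 4.1: "For the purpose of this study, a recurrence of MC will be documented as an AE". For Weeks 16 and 20, protocol 6.2.8 says: "It is expected that these visits should be done by telephone". For Week 24, protocol 6.2.9 says: "Collect and record information for new and ongoing AEs, including subject recurrence of MC". It lists no lesion count.

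**AE and SAE summaries.** Protocol 12.1.3.1 ends the treatment-emergent (TEAE) window at the last application. It then promises an SAE summary by arm, severity and relationship without that limit. Protocol 9 collects SAEs from consent to the last visit. SAP 13.1 confines all AE summaries to TEAEs and plans a table of serious TEAEs by system organ class and preferred term. All AEs and all SAEs are still listed. SAP 14 names four changes from the protocol; neither recurrence nor SAEs is among them.

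**Denominator.** SAP 10.1 gives none for recurrence. SAP 6 has a general default of all subjects in the arm, protocol 11.1 leaves it to what suits the analysis, and the title of Table 14.2.3.5 points to subjects who had cleared.

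**The concern.** The recurrence table is there to show whether clearance lasts. Under SAP 10.1 its only input is a measurement that is not scheduled in the second half of the 24-week study, while the protocol collects recurrence over that same period by another route. Following the SAP as written leaves those collected recurrences out of the endpoint.

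The AE tables offer no second chance. A recurrence AE that starts after the last application is not treatment-emergent, so it reaches a listing and no by-arm table. SAP 6 requires narratives for SAEs and a few named events; recurrence is not one of them.

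The SAE point has the same root. The protocol promises a by-arm summary of SAEs, and the SAP reduces it to those with onset or worsening by the last application. It also drops the breakdown by severity and relationship, and does not declare the change.

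At stake are the description of how durable clearance is and the by-arm view of safety after treatment. The confirmatory tests are not involved.

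**Working it through.** **1. The planning figures.** SAP 5 assumes 227 SB206 and 113 vehicle subjects and two-sided alpha 0.05. With a pooled-variance normal approximation, power = Φ[(d − 1.96·SE0)/SE1], where SE0 = √[p̄(1−p̄)(1/113 + 1/227)] and SE1 = √[p1(1−p1)/113 + p2(1−p2)/227].

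For 18% against 36%: p̄ = 0.300, SE0 = 0.0528, SE1 = 0.0482, and (0.18 − 0.1034)/0.0482 = 1.59, so power is 94.4% (stated 94%). The other two scenarios give 93.4% (stated 93%) and 82.8% (stated 83%). The planning rates can be used as they stand.

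**2. Subjects clear at Week 12 with no later scheduled count.** Number = 227·p(SB206) + 113·p(vehicle).

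| Scenario (vehicle, SB206) | SB206 | Vehicle | Total | Share of 340 |
|---|---|---|---|---|
| 18%, 36% | 81.7 | 20.3 | 102.1 | 30.0% |
| 20%, 38% | 86.3 | 22.6 | 108.9 | 32.0% |
| 20%, 35% | 79.5 | 22.6 | 102.1 | 30.0% |

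These are all the planned Week 12 responders. They are the subjects in whom a later recurrence could be missed, not a number of missed recurrences.

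**3. Share of the time after clearance that scheduled counts cover.** For first clearance at week w, the share to Week 24 is (12 − w)/(24 − w).

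| First clear at | Covered weeks | Share |
|---|---|---|
| Week 12 | 0 of 12 | 0% |
| Week 8 | 4 of 16 | 25% |
| Week 4 | 8 of 20 | 40% |
| Week 2 | 10 of 22 | 45% |

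An unscheduled count could add to this. However, the last analysis window in SAP 7 closes at Day 98, so a later unscheduled count has no analysis visit to be assigned to.

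**4. Direction and possible size.** Subjects counted under SAP 10.1 are a subset of those with either a later positive count or a recurrence AE, so on any given denominator the SAP proportion cannot exceed the combined one. The documents give no recurrence rate. If 5%, 10%, 20% or 30% of the 102 responders in the main scenario recurred after Week 12 (an assumption), about 5, 10, 20 or 31 recurrences would escape scheduled counts.

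**5. Why the denominator matters.** Suppose 10% of cleared subjects recur in each arm (an assumption). Among cleared subjects the rates are equal. Over all randomised subjects they are 0.10 × 36% = 3.6% on SB206 and 0.10 × 18% = 1.8% on vehicle, a doubling produced only by the higher clearance on SB206.

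**6. Time outside the AE and SAE summaries.** From Day 1 to Day 169 there are 168 days; days after the last application = 169 − last application day.

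| Last application | Days outside | Share of 168 |
|---|---|---|
| Day 85 | 84 | 50% |
| Day 57 | 112 | 67% |
| Day 29 | 140 | 83% |

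The last two rows are subjects who stop early and do not restart, which the protocol allows on clearance.

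**The case against.** Five points can be made for the plan.

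- **The protocol is not uniform on Week 24.** Its synopsis and SAP 4 say the Week 24 visit assesses recurrence, and their scar paragraphs, which cover Week 24, contain an undated instruction to count active lesions. A count made then would satisfy SAP 10.1. But Table 1, 6.2.9 and 7.1.1 schedule no such count, and an undated sentence does not create one. At best the documents disagree, which also needs settling.
- **A count by a trained evaluator is more objective than a telephone report.** This stands. Some follow-up reports may also be collected after the Week 12 unblinding. It is a reason to show the two sources separately, not to drop one.
- **The TEAE cut-off is the protocol's own.** This stands. The SAP is not at fault for its TEAE tables, and a table of non-serious AEs after treatment is a request for more, not a correction. The SAE sentence in protocol 12.1.3.1 carries no such limit, so the narrowing there belongs to the SAP.
- **Little may be lost in practice.** All SAEs are listed and receive narratives, and protocol 1.1.4 reports none among 256 Phase 2 subjects. The practical effect may well be small, but the departure from the protocol is still undeclared.
- **The eCRF and table shells may settle details.** They are separate files and were not available. SAP 6 does say that follow-up data will be analysed, but it names no recurrence or AE output, whereas SAP 10.1 expressly takes household spread and scarring to Week 24.

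**Conclusion.** The concern holds. Under SAP 10.1, a recurrence after Week 12 that the protocol collects as an AE enters the recurrence proportion only through a chance unscheduled count, and SAP 13.1 keeps it out of the by-arm AE tables. SAP 13.1 also narrows the protocol's SAE summary without an entry in SAP 14.

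On the planning assumptions, the gap concerns 79 to 86 SB206 and 20 to 23 vehicle subjects clear at Week 12. Subjects who clear earlier have at most 45% of their later follow-up covered by scheduled counts. The bias in the recurrence proportion is towards understatement; its size is unknown because the documents give no recurrence rate.

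This should be corrected, but it is not critical. Recurrence is exploratory, and the primary and secondary tests and their power do not change.

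**What to change.** **SAP 10.1.** Define recurrence as a lesion count above 0 at a later visit, or an AE of MC recurrence through Week 24/ET2, among subjects who reached a count of 0 by Week 12. State that group as the denominator. Report count-based and AE-reported recurrences separately, noting that Weeks 16 and 20 are telephone reports and that some follow-up data may be collected after the Week 12 unblinding.

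**SAP 13.1.** Keep the TEAE tables. Summarise all SAEs by arm, severity and relationship, as protocol 12.1.3.1 states, through Week 24/ET2 to match the collection period in protocol 9. A by-arm table of AEs starting after the last application through Week 24/ET2, with recurrence AEs shown separately, would be useful; it is optional, and the other changes do not depend on it.

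**SAP 14.** Record these changes.

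**Cost.** A few descriptive tables from data already collected, and one SAP revision. Reported recurrence and AE rates may rise by an amount that cannot be predicted. The protocol's TEAE definition and the primary and secondary analyses stay as they are.
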